#### **6.1.4.1.1. Interruption of Hu5F9-G4 Treatment**

For patients who experience dose interruptions, instructions for repriming are provided in [Section 6.1.3](#).

#### **6.1.4.1.2. Maintenance Dose Schedule Modification**

Patients who have completed at least 8 weeks of weekly maintenance therapy may stay at the same infusion dose, but may have their Hu5F9-G4 schedule of administration extended to every 2 or 3 weeks, if supported by PK data and approved by the CTSC.

#### **6.1.4.1.3. Intra-patient Dose Escalation**

In the Phase 1b part of the study, patients who have been on study for at least 8 weeks may have their maintenance dose escalated to a higher dose level that has been previously demonstrated to be safe in this study, at the discretion of the Investigator and the CTSC.

### **6.1.4.2. Cetuximab**

#### **6.1.4.2.1. Administration**

Cetuximab should not be given as an intravenous push or bolus; instead, it should be administered by infusion pump or syringe pump at an infusion rate that should not exceed 10 mg/min. It should also be administered through a low protein binding 0.22-micrometer in-line filter. The parenteral drug product should be inspected visually for particulate matter and discoloration prior to administration, whenever solution and container permit. The solution should be clear and colorless and may contain a small amount of easily visible, white, amorphous, cetuximab particulates. Do not shake or dilute the solution.

#### **6.1.4.2.2. Infusion Reactions**

Serious infusion reactions requiring medical intervention and immediate, permanent discontinuation of cetuximab included rapid onset of airway obstruction (bronchospasm, stridor, hoarseness), hypotension, shock, loss of consciousness,

myocardial infarction, and/or cardiac arrest. Severe (NCI CTCAE Grades 3 and 4) infusion reactions occurred in 8.4% of 1373 patients receiving cetuximab in 4 different clinical studies, with a fatal outcome in 1 patient (Cetuximab [Erbitux®] Prescribing Information, [Appendix A](#)). Approximately 90% of severe infusion reactions occurred with the first infusion despite premedication with antihistamines.

Patients should be monitored for 1 hour following cetuximab infusion in a setting with resuscitation equipment and other agents necessary to treat anaphylaxis (e.g., epinephrine, corticosteroids, intravenous antihistamines, bronchodilators, and oxygen). If serious infusion reactions occur, study drug administration should be immediately interrupted and permanently discontinued. If hypersensitivity or infusion-related events develop, the infusion rate should be reduced by 50% for NCI CTCAE Grade 1 or 2 and non-serious NCI CTCAE Grade 3 infusion reactions. Patients who experience infusion reactions must be observed until resolution of the event.

#### **6.1.4.2.3. Cardiopulmonary Arrest**

Cardiopulmonary arrest and/or sudden death occurred in 4 (2%) of 208 patients treated with radiation therapy and cetuximab as compared to none of 212 patients treated with radiation therapy alone (Cetuximab [Erbitux®] Prescribing Information, Appendix A). Carefully consider the use of cetuximab in combination with radiation therapy or platinum-based therapy with 5-FU in head and neck cancer patients who have a history of coronary artery disease, congestive heart failure, or arrhythmias in light of these risks. Closely monitor serum electrolytes, including serum magnesium, potassium, and calcium, during and after cetuximab infusion.

#### **6.1.4.2.4. Pulmonary Toxicity**

Interstitial lung disease (ILD), including 1 fatality, occurred in 4 of 1570 (< 0.5%) patients receiving cetuximab in 3 clinical trials (Cetuximab [Erbitux®] Prescribing Information, Appendix A), as well as in other studies in colorectal cancer and head and neck cancer. Monitor patients for signs and symptoms of pulmonary toxicity and

interrupt cetuximab for acute onset or worsening of pulmonary symptoms and permanently discontinue cetuximab for confirmed ILD.

#### **6.1.4.2.5. Dermatologic Toxicity**

Dermatologic toxicities, including acneiform rash, skin drying and fissuring, paronychial inflammation, infectious sequelae (for example, *S. aureus* sepsis, abscess formation, cellulitis, blepharitis, conjunctivitis, keratitis/ulcerative keratitis with decreased visual acuity, cheilitis), and hypertrichosis occurred in patients receiving cetuximab therapy. Acneiform rash occurred in 82% of 1373 patients receiving cetuximab in 4 clinical trials (Cetuximab [Erbitux®] Prescribing Information, [Appendix A](#)). Severe acneiform rash occurred in 9.7% of patients.

Acneiform rash usually developed within the first 2 weeks of therapy and resolved in a majority of the patients after cessation of treatment, although in nearly half, the event continued beyond 28 days. Life-threatening and fatal bullous mucocutaneous disease with blisters, erosions, and skin sloughing has also been observed in patients treated with cetuximab. It could not be determined whether these mucocutaneous adverse reactions were directly related to EGFR inhibition or to idiosyncratic immune-related effects (e.g., Stevens-Johnson syndrome or toxic epidermal necrolysis). Prophylactic interventions for cetuximab skin rash using oral and/or topical antibiotics, sun block, moisturizing creams, or other agents may be instituted according to local standard of care. Possible oral antibiotic regimens for skin prophylaxis include oral doxycycline 100 mg twice-weekly or comparable regimens with tetracycline or minocycline. Patients will be monitored for dermatologic toxicities and infectious sequelae and they will be instructed to limit sun exposure during cetuximab therapy.

Recommended dose modifications for severe (NCI CTCAE Grade 3 or 4) acneiform rash are specified in [Table 3](#).

**Table 3. Cetuximab Dose Modification Guidelines for Rash**

Severe Acneiform Rash	Cetuximab	Outcome	Cetuximab Dose Modification
First occurrence	Delay infusion 1 to 2 weeks	Improvement	Continue at 250 mg/m 
		No Improvement	Discontinue cetuximab
Second occurrence	Delay infusion 1 to 2 weeks	Improvement	Continue at 200 mg/m 
		No Improvement	Discontinue cetuximab
Third occurrence	Delay infusion 1 to 2 weeks	Improvement	Continue at 150 mg/m 
		No Improvement	Discontinue cetuximab
Fourth occurrence	Discontinue cetuximab		

Source: Cetuximab (Erbitux®) Prescribing Information ([Appendix A](#)).

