**Table 1. Phase 1b Dose Levels and Schedule**

Dose Cohort	Drug/Dose (Intravenous)	Dose Schedule (Day per 28-day Cycle)	
		Cycle 1	Cycle 2+
1	Hu5F9-G4 1 mg/kg (prime)	Day 1	—
	Hu5F9-G4 10 mg/kg (maintenance)	Day 8, 15, 22	Day 1, 8, 15, 22
	Cetuximab 300 mg/m  (load)	Day 8	
	Cetuximab 200 mg/m  (maintenance)	Day 15, 22	Day 1, 8, 15, 22
2	Hu5F9-G4 1 mg/kg (prime)	Day 1	—
	Hu5F9-G4 10 mg/kg (maintenance)	Day 8, 15, 22	Day 1, 8, 15, 22
	Cetuximab 400 mg/m  (load)	Day 8	
	Cetuximab 250 mg/m  (maintenance)	Day 15, 22	Day 1, 8, 15, 22
3	Hu5F9-G4 1 mg/kg (prime)	Day 1	—
	Hu5F9-G4 20 mg/kg (maintenance)	Day 8, 15, 22	Day 1, 8, 15, 22
	Cetuximab 400 mg/m  (load)	Day 8	
	Cetuximab 250 mg/m  (maintenance)	Day 15, 22	Day 1, 8, 15, 22
4 a	Hu5F9-G4 1 mg/kg (prime)	Day 1	—
	Hu5F9-G4 30 mg/kg (maintenance) b	Day 8, 15, 22	Day 1, 8, 15, 22
	Cetuximab 400 mg/m  (load)	Day 8	—
	Cetuximab 250 mg/m  (maintenance)	Day 15, 22	Day 1, 8, 15, 22
5	Hu5F9-G4 1 mg/kg (prime)	Day 1	—
	Hu5F9-G4 45 mg/kg (maintenance)	Day 8, 15, 22	Cycle 2: Day 1, 8, 15, 22 Cycle 3+: Day 1 and 15
	Hu5F9-G4 45 mg/kg (loading)	Day 11	
	Cetuximab 400 mg/m  (load)	Day 8	—
	Cetuximab 250 mg/m  (maintenance)	Day 15, 22	Day 1, 8, 15, 22

a The Hu5F9-G4 loading dose was not administered in Cohort 4. Potential loading dose cohort may be added if deemed necessary by the Clinical Trial Steering Committee (CTSC).

b As recommended by CTSC, a 30-mg maintenance dose was administered in Cohort 4.

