## 6. TREATMENT PLAN

### 6.1. Study Drug Administration Guidance: Hu5F9-G4 and Cetuximab

#### 6.1.1. Dosing

Planned Phase 1b dose levels are presented in [Table 1](#) and the Phase 2 dose and schedule is presented in [Table 2](#).

The dose of each study drug will be calculated based on actual weight at enrollment (using weight obtained either at Screening or on Day 1) and remains constant throughout the study, unless there is a > 10% change in weight from baseline. Modifications to the study drug doses administered should be made for a > 10% change in body weight and for dose modifications as described in [Section 6.1.4](#). Dose modifications for changes in body weight < 10% may be made according to local institutional guidelines.

All patients will receive an Hu5F9-G4 priming dose of 1 mg/kg on Day 1.

The duration of the infusion of the priming dose will be 3 hours ( $\pm$  30 minutes).

The priming dose will be followed by a weekly maintenance dose. The duration of the infusion of the maintenance dose will be 2 hours ( $\pm$  30 minutes). The first maintenance dose will be administered starting on Day 8 after the completion of the first dose of cetuximab. All subsequent maintenance doses of Hu5F9-G4 will be administered at the start of each study week ( $\pm$  1 day). Hu5F9-G4 will be administered at least 1 hour after the completion of cetuximab administration.

All patients should be monitored for at least 1 hour post-infusion for the first 4 weeks.

Post-infusion monitoring should begin after the last study drug is given.

Post-infusion monitoring is not required for doses after Cycle 1. Patients who experience any treatment-related AEs during the observation period should be further monitored, as clinically appropriate.

Patients will receive a cetuximab dose of 300-400 mg/m^2 given IV starting on Day 8, followed by weekly dosing at 200-250 mg/m^2 on Days 15 and 22. Starting at

Cycle 2, and for each cycle thereafter, cetuximab will be given weekly starting on Day 1. (Details are provided in [Section 6.1.4.2.](#))

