#### **6.1.4. Dose Delays, Dose Modifications, and Safety Management Guidelines**

##### **6.1.4.1. Hu5F9-G4**

Dose modification or dose delay of Hu5F9-G4 may not occur for patients in the initial 28-day DLT assessment period in the Phase 1b part of the study or for patients in the first cycle of the Phase 2 part of the study. After the initial 28-day treatment period for evaluation of DLTs, Hu5F9-G4 may be withheld if treatment-emergent Hu5F9-G4-related AEs occur, which include all AEs that constitute a DLT as defined in [Section 3.2.4](#). If the severity has recovered to Grade 0 to 2 within 4 weeks and in the absence of disease progression, Hu5F9-G4 may be re-introduced at the next lower dose level. Patients who experience a DLT of either hemolytic anemia or Grade  $\geq 4$  non-hematological toxicity will not restart Hu5F9-G4 and will be withdrawn from study drug treatment. Restarting treatment after a delay of more than 4 weeks (such as for an unrelated medical condition with expected recovery) must be approved by the medical monitor.

Patients with an interruption or treatment delay of longer than 2 weeks after receiving only the priming dose (1 mg/kg) or  $>4$  weeks after receiving at least 1 maintenance dose (e.g., 30 mg/kg) must be “reprimed” by receiving the priming dose of 1 mg/kg IV over 3 hours ( $\pm 30$  minutes) and 3 subsequent weekly maintenance doses following the repriming dose prior to resuming the Q2W dosing schedule ([Section 6.1.3](#), Repriming).

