| 1 | 5F9 1 mg/kg | 5F9 10 mg/kg + Cetuximab 300 mg/m ² | 5F9 10 mg/kg + Cetuximab 200 mg/m ² | QW |
| 2 | | 5F9 10 mg/kg + Cetuximab 400 mg/m ² | 5F9 10 mg/kg + Cetuximab 250 mg/m ² | |
| 3 | | 5F9 20 mg/kg + Cetuximab 400 mg/m ² | 5F9 20 mg/kg + Cetuximab 250 mg/m ² | |
| 4 | | 5F9 30 mg/kg + Cetuximab 400 mg/m ² | 5F9 30 mg/kg + Cetuximab 250 mg/m ² | |
| 5 ^b | | 5F9 45 mg/kg + Cetuximab 400 mg/m ² | 5F9 45 mg/kg + Cetuximab 250 mg/m ² | C2: QW C3+: Q2W |

Abbreviations: C = cycle; QW = every week; Q2W = every 2 weeks.

a Cetuximab is given on a weekly schedule.

b A loading dose of 5F9 at 45 mg/kg is given on Day 11.

The dose levels and schedules for 5F9 in each cohort are described in [Table 2](#), in combination with cetuximab (a loading dose of 400 mg/m² followed by a maintenance dose of 250 mg/m² QW) in Phase 2.

Table 2 Study Treatment Dose and Schedule for Phase 2

| Cohort | 5F9 Dose Levels in Cycle 1 | | | 5F9 Schedule in Cycle 2 ^a |
|-----------------------------|-----------------------------|--|---|--------------------------------------|
| | Day 1 (5F9 priming dose) | Day 8 (5F9 maintenance dose + cetuximab loading dose) | Day 15, 22 (maintenance dose) | |
| KRASwt | 5F9 1 mg/kg | 5F9 30 mg/kg + Cetuximab 400 mg/m ² | 5F9 30 mg/kg + Cetuximab 250 mg/m ² | Q2W |
| KRASm Cohort 1 | | | | |
| KRASm Cohort 2 ^b | | 5F9 45 mg/kg + Cetuximab 400 mg/m ² | 5F9 45 mg/kg + Cetuximab 250 mg/m ² | C2: QW C3+: Q2W |

Abbreviations: C = cycle; KRASm = KRAS mutant; KRASwt = KRAS wild-type; QW = every week; Q2W = every 2 weeks.

a Cetuximab is given on a weekly schedule.

b A loading dose of 5F9 at 45 mg/kg is given on Day 11.

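### The cetuximab rash table gives only absolute doses built on 250 mg/m² maintenance, so for Cohort 1 (200 mg/m²) the step after a first severe rash is a 25% dose increase

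*Protocol*

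**What the plan says.** Section 6.1.4.2.5 of the protocol sends sites to Table 3 for dose changes after Grade 3 or 4 acneiform rash. After a delay of 1 to 2 weeks, a patient whose rash has improved resumes at a fixed dose: "Continue at 250 mg/m"² after the first occurrence, "Continue at 200 mg/m"² after the second and "Continue at 150 mg/m"² after the third. (The quoted words stop just before the superscript.) A fourth occurrence ends cetuximab. The table cites the cetuximab prescribing information as its source. It has no footnote, percentage, cohort restriction or reference to the patient's assigned dose.

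Two maintenance doses are in use. Protocol Table 1 lists "Cetuximab 200 mg/m"² for Cohort 1, on Days 15 and 22 of Cycle 1 and weekly from Cycle 2. Synopsis Table 2 agrees, and SAP Table 1 shows the same Cycle 1 maintenance dose, "5F9 10 mg/kg + Cetuximab 200 mg/m"². Cohorts 2 to 5 and Phase 2 get 250 mg/m².

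Section 6.1.1 recognises both levels ("followed by weekly dosing at 200-250 mg/m"²). It refers sites to Section 6.1.4 for dose modifications and to Section 6.1.4.2 for cetuximab details.

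**The concern.** The values in Table 3 make a sensible reduction ladder only for someone on 250 mg/m²: no change, then two reductions. Applied to a patient on 200 mg/m², the first entry is above the assigned dose. Taken at its word, the table raises the dose of the drug that has just caused a severe toxicity.

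Section 1.5.2 explains that cetuximab was started below the approved dose because the adverse-effect profile of the combination was unknown. Full dose was to follow in the second cohort if the reduced dose was well tolerated. The literal step undoes that reduction for an individual patient at the point where tolerability is in doubt. What is at stake is the safety of a few patients, not an endpoint or an analysis.

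**Working it through.** **Inputs**

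- Post-rash doses: 250, 200 and 150 mg/m² (Table 3).
- Assigned maintenance: 200 mg/m² in Cohort 1; 250 mg/m² in Cohorts 2 to 5 and Phase 2 (protocol Tables 1 and 2; SAP Tables 1 and 2).
- Approved doses: 400 mg/m² load, then 250 mg/m² weekly (Section 1.5.2).
- Cohort size: 3 to 6, plus up to 6 on expansion (Section 3.2.2).
- Severe acneiform rash: 9.7% of cetuximab patients in earlier trials (Section 6.1.4.2.5).

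**The plan's own figure.** Section 1.5.2 gives the Cohort 1 reductions as 25% (load) and 20% (weekly). These reproduce: 1 - 300/400 = 25% and 1 - 200/250 = 20%.

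**Step change.** Change = Table 3 dose / assigned dose - 1.

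| Severe rash that improves | Table 3 dose (mg/m²) | Assigned 250 | Assigned 200 (Cohort 1) |
|---|---|---|---|
| First | 250 | 250/250 - 1 = 0% | 250/200 - 1 = +25% (+50 mg/m²) |
| Second | 200 | 200/250 - 1 = -20% | 200/200 - 1 = 0% |
| Third | 150 | 150/250 - 1 = -40% | 150/200 - 1 = -25% (-50 mg/m²) |

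**Does another section supply the missing steps?**

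- The rest of Section 6.1.4.2 gives no step for 200 mg/m².
- Section 6.1.5.1 refers to the prescribing information, which is Table 3's own source.
- Section 6.1.4.1 concerns the other drug. It does word the restart relative to the patient's own level ("Hu5F9-G4 may be re-introduced at the next lower dose level"), which Table 3 does not.
- Section 3.2.1 caps cetuximab at the recommended single-agent dose. A dose of 250 mg/m² does not breach that cap, so the cap does not block the increase.
- The 3+3 rule in Section 3.2.2 governs cohorts and escalation, not one patient's next cetuximab dose.

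**Which rashes are concerned?** Under Section 6.1.4.1, a Grade 4 non-hematological DLT leads to withdrawal from study treatment, so the gap mainly concerns Grade 3.

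**How many patients?** Assume the 9.7% rate also holds at 200 mg/m² in this combination. The expected number reaching the first step is n × 0.097, and the chance of at least one is 1 - 0.903ⁿ.

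| n | Expected | Chance of at least one |
|---|---|---|
| 3 | 0.29 | 26% |
| 6 | 0.58 | 46% |
| 12 | 1.16 | 71% |

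These cover the whole treatment course. The number still to come at Amendment 3 is lower, and the documents do not allow it to be estimated.

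**The case against.** The strongest reply is that nobody may be left to harm. Cohort 4 dosing is reported in the past tense (Table 1, footnote b), and the Phase 2 dose has already been chosen from Phase 1b data (Section 1.5.1.2). Because each cohort must finish its DLT period before escalation (Section 3.2.3), Cohort 1 must already have cleared. The literal step would also put a Cohort 1 patient on Hu5F9-G4 10 mg/kg with cetuximab 250 mg/m², which is the Cohort 2 maintenance regimen and had to be passed before Cohorts 3 and 4. Patients on study for 8 weeks may in any case move to the Phase 2 regimen, which uses 250 mg/m² (Section 3.4). All of this stands, and it keeps the point minor. It does not make a dose increase after a severe rash correct. The protocol still carries the Cohort 1 regimen and never says that no patient remains on 200 mg/m².

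A second reply is that the table is headed as guidelines, its contents are only recommended, and the verb implies no change at the first step. Many investigators would indeed resume at 200 mg/m². But the same verb introduces 200 and 150, which are reductions for a patient on 250, so it cannot settle the reading. If the first step is taken as staying at 200, the second step then gives no reduction.

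A third reply is oversight. Rash usually appears within 2 weeks of starting cetuximab, so from a Day 8 start a typical first occurrence falls inside the 28-day DLT window. A related Grade 3 rash is not among the DLT exceptions (Section 3.2.4), so the steering committee would see it. That makes unnoticed harm less likely, but it does not set the patient's next dose. The supervised rule for raising a patient's dose (Section 6.1.4.1.3) sits under the Hu5F9-G4 heading and does not govern cetuximab.

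The patient counts are also open to challenge: the 9.7% comes from other cetuximab trials, and nothing indicates that Cohort 1 was expanded to 12. They should be read as an upper range.

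**Conclusion.** The concern holds, as a minor patient-safety point. For the 200 mg/m² regimen that the protocol still lists, Table 3 as written gives +25%, 0% and -25% of the assigned dose, where a patient on 250 mg/m² gets 0%, -20% and -40%. The arithmetic is certain. That the table presumes 250 mg/m² is an inference, but a well-supported one: the table is taken from the prescribing information, and Section 1.5.2 gives 250 mg/m² as the approved weekly dose. The practical consequence is limited to Cohort 1 and depends on whether anyone is still on 200 mg/m², which the documents do not say.

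**What to change.** Reword the first-occurrence entry so that the patient resumes at the assigned maintenance dose, and state that the resumed dose may not exceed the dose assigned when the rash occurred. The sponsor should set the reduction steps below 200 mg/m². Two possible ladders, neither given in the documents, are 200, 160, 120 mg/m² (the table's own 100%, 80%, 60% applied to 200) and 200, 150, 100 mg/m² (steps of 50). Under either one the first step becomes 0% instead of +25%.

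If the sponsor confirms that no patient remains on 200 mg/m² and none will be added, a footnote saying that Table 3 applies to 250 mg/m² maintenance is enough. The cost is one table edit or footnote in the next amendment, with no added patients, visits or procedures.

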#### **6.1.4.2.6. Hypomagnesemia and Electrolyte Abnormalities**

In patients evaluated during clinical trials, hypomagnesemia occurred in 55% of 365 patients receiving cetuximab in one trial (Appendix A) and it was severe (NCI CTCAE Grades 3 and 4) in 6%–17%. In one study in which cetuximab was administered in combination with platinum-based therapy, the addition of cetuximab to cisplatin and 5-FU resulted in an increased incidence of hypomagnesemia (14% vs. 6%) and of Grade 3–4 hypomagnesemia (7% vs. 2%) compared to cisplatin and 5-FU alone. In contrast, the incidences of hypomagnesemia were similar for those who received cetuximab, carboplatin, and 5-FU compared to carboplatin and 5-FU (4% vs. 4%). No patient experienced Grade 3–4 hypomagnesemia in either arm in the carboplatin subgroup. The onset of hypomagnesemia and accompanying electrolyte abnormalities occurred days to months after initiation of cetuximab. Periodically monitor patients for hypomagnesemia, hypocalcemia, and hypokalemia, during and for at least 8 weeks following the completion of cetuximab.

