## **6.2. Post-therapy Follow-up and Patient Study Completion**

Patients who complete, terminate, or decline further treatment should be encouraged to return for an End of Treatment Visit for evaluation of safety within 1 week of the decision to end Hu5F9-G4 treatment. The studies to be performed at end of treatment are listed in the Schedules of Assessments (SOAs), [Section 7.4](#). It is strongly encouraged that patients return for their Safety Follow-up Visit 30 days ( $\pm$  1 week) after the last dose of last study drug received. The Safety Follow-up Visit assessments are described in [Section 7.5](#).

Patients are considered to have completed study drug treatment when they finish the Safety Follow-up Visit 30 days ( $\pm$  1 week) after their last dose of the last study drug received, unless they are experiencing ongoing drug-related AEs and serious adverse events (SAEs). For patients being followed for ongoing AEs or SAEs, follow-up visits will continue at least every 4 weeks until resolution to baseline or stabilization of these events, unless the patient starts another anti-cancer therapy. Follow-up for ongoing AEs or SAEs after the Safety Follow-up Visit will stop if a patient begins another anti-cancer therapy.

All patients, including those who discontinue study treatment early, will be followed for response until progression and for survival for 5 years from the date of enrollment. For any patient who dies during this period, the cause of death must be reported to the Sponsor. Patients are considered to have completed study participation when they are no longer followed for disease progression or survival.

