**Table 6. Post-treatment Assessments, Phase 1b and Phase 2**

Examination	Study 5F9004, Post-treatment Assessments: Phase 1b/2 Solid Tumor/CRC Trial of Hu5F9-G4 + Cetuximab			
Cycle (28-day cycles)	End of Treatment	Safety Follow-up	Long-term Follow-up	Survival Follow-up
	Within 1 Week of EOT Decision	30 Days after Last Dose of study drug	Until disease progression or new anti-cancer therapy	Up to 60 months from date of LPE
Visit Window		± 1 Week	± 2 Weeks	± 1 Month
Assessments				
Serum or urine pregnancy test		X		
CBC w differential, platelets, reticulocyte count		X		
Peripheral blood smear		X		
Serum chemistry		X		
Haptoglobin, D-Dimer, thrombin time, and plasma fibrinogen		X		
PT/INR, aPTT		X		
Pharmacokinetics	X a	X a		
Correlative studies	X		X b	
Antidrug Antibodies	X	X		
CD47 Receptor Occupancy	X c			
ECOG performance status		X		
Vital signs		X		
Physical examination (symptom directed)		X		
PPD				
Response assessment	X e	X d,e	Q8W b	
Adverse events	X	X	Q4W b	
Concomitant medications	X	X		
Survival follow-up and new anti-cancer therapy				Q3M

Abbreviations: aPTT = activated partial thromboplastin time; CBC = complete blood count; CRC = colorectal cancer; DLT = dose-limiting toxicity; ECOG = Eastern Cooperative Oncology Group; EOT = End of Treatment Visit; INR = international normalized ratio; LPE = last patient enrolled; M = month(s); PT = prothrombin time' W = week(s).

- Required only in Phase 1b.
- Details provided in [Section 7.6](#).
- Sample to be collected only if the visit occurs prior to Cycle 2. Samples are collected only for Phase 1b, Cohorts 1 to 4.
- Required only if not completed within the 4 weeks prior to the Safety Follow-up Visit.
- Details provided in [Section 10](#).

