## **7.4.      End of Treatment Visit**

End of Treatment Visit to be completed within 1 week of the decision to end treatment with Hu5F9-G4.

- Pharmacokinetic sample collection (for Phase 1b only). PK samples will be collected for Hu5F9-G4 and cetuximab.
- Correlative Studies
- Antidrug Antibodies
- CD47 Receptor Occupancy (only if End of Treatment Visit occurs prior to Cycle 2).
- Response Assessment, if not performed within the last 4 weeks. (Details are provided in [Section 10](#))
- Adverse Events
- Concomitant medications

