### **7.5. Safety Follow-up Visit**

Safety Follow-up visit to be completed within 30 days ( $\pm$  1 week) after the last dose of Hu5F9-G4.

- Local Laboratory
  - CBC (w differential, platelets, reticulocyte count)
  - Serum chemistry
  - Haptoglobin, D-Dimer, thrombin time, and plasma fibrinogen
  - PT/INR, aPTT
- Local laboratory Peripheral Blood Smear
- Serum or urine pregnancy test (in women of childbearing potential)
- Pharmacokinetic sample collection for Hu5F9-G4 and cetuximab
- Antidrug Antibodies
- ECOG performance status [Appendix C](#)
- Vital signs
  - blood pressure
  - pulse
  - respiration
  - temperature
  - weight

- Adverse Events
- Concomitant medications
- Physical examination (symptom-directed)
- Response Assessment ( $\pm$  1 week), if not performed within the last 4 weeks  
([Section 10](#))

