## 7.6. Long-term Follow-up

Patient will be followed until disease progression or until they begin a new anti-cancer therapy.

- Response assessment ( $\pm$  1 week), every 8 weeks (Section 10)
- Correlative studies

For patients who achieve a partial or complete response while on study, a repeat disease assessment will be obtained at the time of disease progression whenever possible. These assessments include:

- Blood sample for correlative studies
- PPD

Following the Safety Follow-up Visit, patients with ongoing drug-related AEs and SAEs will be followed for safety. If any study drug-related AEs or SAEs are ongoing after the Safety Follow-up Visit, follow-up with the patient will occur at least every 4 weeks until resolution to baseline or stabilization of these events, unless the patient starts another anti-cancer therapy. Follow-up will stop when a patient begins another anti-cancer therapy.

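### Unless Hu5F9-G4 outlasts cetuximab by about three to five weeks, the visit schedule ends chemistry before the protocol's 8-week electrolyte monitoring floor

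*Protocol*

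**What the plan says.** **The instruction.** Protocol Section 6.1.4.2.6, among the cetuximab safety management guidelines, reads: "Periodically monitor patients for hypomagnesemia, hypocalcemia, and hypokalemia, during and for at least 8 weeks following the completion of cetuximab". It gives a minimum duration but no test frequency, and it does not refer to the schedule of assessments.

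**The schedule after treatment.**
- End of Treatment (Section 7.4): "End of Treatment Visit to be completed within 1 week of the decision to end treatment with Hu5F9-G4". Its list contains no chemistry.
- Safety Follow-up (Section 7.5, Table 6): serum chemistry is listed. Under Table 11 the panel includes magnesium, calcium and potassium. The Table 6 column is headed "30 Days after Last Dose of study drug", with a window of ± 1 week.
- Long-term Follow-up (Section 7.6): "Patient will be followed until disease progression or until they begin a new anti-cancer therapy". Response is assessed every 8 weeks; no chemistry is listed.
- Survival Follow-up (Section 7.7): contact every 3 months, possibly by telephone; no chemistry.

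**The starting point of the 30 days.** Section 7.5 has "Safety Follow-up visit to be completed within 30 days" (± 1 week) "after the last dose of Hu5F9-G4". Section 6.2 counts the same visit from a different point: "after the last dose of last study drug received". The AE reporting period in Section 9.2.1 also runs from the last study drug received.

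**The concern.** The text sets an 8-week minimum, and the table that sites work from ends chemistry well before it. A coordinator who books visits from Table 6 has nothing to prompt a later test, so a low magnesium, calcium or potassium in the second month after cetuximab could go unnoticed.

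The protocol itself treats the risk as real. Section 6.1.4.2.6 cites hypomagnesemia in 55% of 365 cetuximab patients in one trial, severe in 6% to 17%, with onset days to months after cetuximab is started. Section 6.1.4.2.3 separately asks for close electrolyte monitoring during and after infusion. None of these rates is specific to the weeks after cetuximab ends.

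The second problem is that Section 7.5 counts from Hu5F9-G4 alone. If cetuximab is the later drug, that wording moves the only post-treatment chemistry closer to the last cetuximab dose.

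**Working it through.** No statistical calculation applies; this is calendar arithmetic on the protocol's own intervals. Days are counted from the last cetuximab dose.

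**Inputs**
- Monitoring floor: 8 weeks × 7 = 56 days (Section 6.1.4.2.6).
- Safety Follow-up: 30 ± 7 days, so Day 23 to 37 after its starting point (Table 6, Sections 6.2 and 7.5).
- Other post-treatment chemistry: none (Sections 7.4, 7.6, 7.7; Table 6).
- Phase 2 dosing at 30 mg/kg from Cycle 2: cetuximab on Days 1, 8, 15 and 22; Hu5F9-G4 on Days 1 and 15 (Table 2).

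**1. Both drugs stop together, or cetuximab stops last and Section 6.2 is followed.** The last scheduled chemistry is on Day 23 to 37. Time left before Day 56 with no scheduled test:
- latest visit: 56 − 37 = 19 days
- nominal visit: 56 − 30 = 26 days
- earliest visit: 56 − 23 = 33 days

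**2. Hu5F9-G4 continues *w* days after cetuximab.** Safety Follow-up falls on Day *w* + 23 to *w* + 37.
- It can reach Day 56 once *w* + 37 ≥ 56, that is *w* ≥ 19.
- It always reaches Day 56 once *w* + 23 ≥ 56, that is *w* ≥ 33.
- Below *w* = 19 the gap is shorter than in step 1 but still there.

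**3. Cetuximab is the later drug and Section 7.5 is followed.** If cetuximab continues *v* days after the last Hu5F9-G4 dose, the visit falls on Day 23 − *v* to 37 − *v*. On the Phase 2 schedule a patient whose last infusion is on Day 8 or Day 22 has *v* = 7 with no departure from plan. The visit is then on Day 16 to 30, and the unscheduled stretch is 56 − 30 = 26 to 56 − 16 = 40 days. Under Section 6.2 the same patient would be seen on Day 23 to 37.

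**4. With one added test on Day 56 to 63.** When both drugs stop together, the two scheduled tests are 56 − 37 = 19 to 63 − 23 = 40 days apart, and the floor is reached. A window of ± 7 days would allow Day 49 and could still miss it.

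**The case against.** The strongest reply is that the protocol does not contradict itself. Section 6.1.4.2.6 is an instruction in its own right, and Table 6 does not cancel it. Other management instructions also sit in prose, such as pulmonary monitoring in Section 6.1.4.2.4. Sites may order unscheduled tests, and Section 12.10 requires results to be entered in the eCRF. Because no frequency is set, no particular test is strictly prescribed. This stands. A reader might infer that the protocol leaves these patients unmonitored after Day 37; the documents do not support that. What they show is a schedule that omits something the text asks for. By contrast, the Hu5F9-G4 hemagglutination monitoring in Section 6.1.5.2.1 is tied expressly to the schedule.

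Second, the clinical gap is narrow. Chemistry is scheduled weekly on treatment, apart from extra visits (Tables 4 and 5), and again at Safety Follow-up. Section 7.6 provides contact at least every 4 weeks "If any study drug-related AEs or SAEs are ongoing after the Safety Follow-up Visit", until resolution or stabilization, unless new therapy starts. From a nominal Day 30 that reaches about Day 58. Drug-related SAEs stay reportable at any time (Section 9.2.1). This also stands in part. The 4-weekly contact applies only to events already present and names no laboratory test, so it is not designed to find a new abnormality.

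Third, Section 7.5 may simply be a wording slip, since Sections 6.2 and 9.2.1 agree on the last study drug. That is probably right, and it is a reason to correct it. A reader could build much larger shifts by assuming that cetuximab continues alone for weeks, which the trial may permit. Those figures would rest on assumed durations and on choosing the one outlying sentence over Section 6.2. Only the 7-day difference follows from the dosing schedule.

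**Conclusion.** The inconsistency is real but conditional. For patients who stop both drugs together, or stop cetuximab last, the final 19 to 33 days of the 8-week period (nominally 26) have no scheduled chemistry when the visit is counted from the last study drug. The gap does not apply to every patient: it can close when Hu5F9-G4 continues 19 days beyond cetuximab and always closes from 33. The documents do not say how often each pattern occurs, and they give no rate of electrolyte events after cetuximab ends, so no number of missed events can be stated.

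The result assumes that monitoring for at least 8 weeks calls for a test at or after Day 56. That is the natural reading of a minimum duration, but the protocol does not spell it out.

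The Section 7.5 starting point is wrong against Sections 6.2 and 9.2.1 and should be corrected whatever is decided about the 8 weeks.

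A reader might go on to infer that the primary results are at risk. They are not: DLTs are judged in the first 4 weeks of treatment and response on imaging, so DLTs, dose selection and ORR are unaffected. Nor does the point justify extending AE collection in Section 9.2.1 past the start of new therapy. That would be a debatable trade-off for one class of event, and closing the schedule gap does not need it. This is a modest safety-schedule correction that should be made.

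**What to change.** 1. **Section 7.5:** count Safety Follow-up from the last dose of the last study drug, as Section 6.2 does. This costs nothing.
2. **Table 6:** add one local magnesium, calcium and potassium test at Day 56 (+7 days) after the last cetuximab dose, cross-referenced to Section 6.1.4.2.6. Waive it if on-treatment, Safety Follow-up or standard-of-care chemistry falls in that window.
3. **Alternative to item 2:** if the sponsor does not intend 8 weeks, correct Section 6.1.4.2.6.

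Leave AE collection in Section 9.2.1 unchanged.

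The cost is one local blood sample for each patient not otherwise tested. Treatment may run until progression (Section 3.9), so some of these patients will already have progressed or started new therapy and would need an extra contact. There is also a small analysis consequence. The worst-grade shift table in SAP Section 6.4 states no cut-off, so the added values would enter it. Values taken after new anticancer therapy should be flagged or left out of that table; the start of such therapy is already collected under Section 7.7.
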